4.2 Exclusion Criteria

An individual who meets any of the following criteria will be excluded from participation in this study:

1. Active systemic or local knee[#] infection
2. Active malignancy
3. Life expectancy less than 6 months
4. Prior ipsilateral knee arthroscopic surgery or repeat TKA (within 9 months of screening)
5. Ipsilateral knee intra-articular injection in the last 3 months
6. Rheumatoid arthritis, spondyloarthropathies, crystal disease, gout, pseudogout, or lupus
7. Pregnant during the study period
8. Renal dysfunction as defined by serum creatinine >1.6 dl/mg or eGFR <60 on blood tests obtained within 30 days of procedure
9. Body weight greater than 200 Kg
10. Known history of severe contrast allergy to iodinated contrast resulting in anaphylaxis
11. Known significant arterial atherosclerosis that would limit selective angiography and/or lower extremity symptoms thought to be secondary to arterial vascular disease (eg claudication, ischemic rest pain)
12. Known avascular necrosis in the target knee
13. Complications of TKA such as suspected or confirmed early loosening, ligamentous instability, reflex sympathetic dystrophy, polyethylene wear with or without particle disease (osteolysis), patellofemoral mal-tracking, referred hip and low back pain, and large effusions** (with or without hemarthrosis) on available imaging studies such as knee radiographs, computed tomography scans, and / or the MRA performed for the study purposes.
14. Patient is enrolled in a different trial for treatment of knee pain post total knee arthroplasty (ipsilateral knee)

using Musculoskeletal Infection Society (MSIS) criteria for diagnosis of prosthetic joint infection

2011 Musculoskeletal Infection Society (MSIS) criteria ^[1]	
PJI is present when 1 major criteria exist or 4 out of 6 minor criteria exist	
Major criteria:	
	
 ■ 2 positive periprosthetic cultures with phenotypically identical organisms ■ A sinus tract communicating with the joint
Minor criteria:	
	
 ■ Elevated CRP and ESR ■ Elevated synovial fluid WBC count or ++ change on leukocyte esterase test strip ■ Elevated synovial fluid PMN% ■ Presence of purulence in the affected joint ■ Positive histologic analysis of periprosthetic tissue ■ A single positive culture

* Patients with contraindications to MRA or gadolinium administration such as claustrophobia, metallic fragment/implants, pacemaker, or severe gadolinium associated contrast allergy can be enrolled and MRA will not be performed in these patients.

** if pain persists after aspiration of a large knee effusion, a potential subject can be enrolled.

Note: Absence of exclusion criteria will be confirmed by orthopedic investigator and / or medical record from available orthopedic surgery notes if within one month of enrollment.

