1.4 Potential Risks & Benefits

1.4.1 Known Potential Risks

Potential AEs related to the use of the device from the device insert of directions for use (DFU) [attachment 1] and recent literature [12, 37-40, 48-53].

- Possible AEs:

- Incomplete occlusion of vascular beds or territories may give rise to the possibility of post-procedural development of alternative vascular pathways, recanalization, or recurrence of symptoms
- Post-embolization syndrome including fever, malaise, headache, and myalgia (body aches)
- Transient, self-resolving cutaneous purpura / skin color change
- Transient plantar or peripheral sensory paresthesia

- Synovitis related symptoms including pain, stiffness or limited joint mobility

- Rare AEs:

- Allergic reaction and foreign body reactions (e.g., pain, rash, fever, inflammation)
- Capillary bed saturation and tissue damage
- Infection
- Neurological deficits
- Thrombosis
- Undesirable reflux, passage/migration or placement of Embozene™ Microspheres, resulting in non-target embolization, ischemia, and / or ischemic infarction.
- Non-target embolization to lower extremity vasculature resulting in vascular thrombosis and limp threatening ischemia
- Vessel or lesion rupture
- Tissue necrosis
- Dermal ulcer
- Tendon or ligament rupture
- Osteonecrosis
- Joint infection
- Syncope due to pain during the study procedures (rare)

- Very rare AEs:

- Death (extremely rare)

Potential AEs associated with angiography and catheterization of vessels:

- Nausea, vomiting, and/or allergic reaction anaphylaxis due to iodinated contrast used during embolization procedure (less possible)
- Contrast-induced renal dysfunction (less possible)
- Access site-related adverse events: bleeding, infection, hematoma formation, arteriovenous fistula, pseudoaneurysm (rare)
- Catheterization-associated adverse events: injury to catheterized vessels including vessel perforation, dissection, vasospasm, or thrombosis (rare)
- Infection (rare)

Potential AEs associated with knee aspiration for biomarker analysis

- Knee infection (rare)
- Bleeding (rare)
- Pain and discomfort

Potential AEs associated with blood draws for biomarker analysis

- Bleeding, bruising
- Pain and discomfort, vasovagal reaction to pain

Potential AEs associated with radiation exposure

- Deterministic radiation risks: Radiation-induced injuries to the skin and underlying tissues, which occur shortly after the exposure (rare)

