- Stochastic radiation risks: Radiation-induced malignancy which may occur later in life (rare)

Potential AEs associated with MRA knee (with contrast):

- Discomfort (possible)
- Anxiety or claustrophobia (less possible)
- Peripheral nerve stimulation causing tingling or twitching (rare)
- Injury and burns related to metals (very rare, particularly with the MR screening performed prior to entering MR zone and subjects with contraindications to MR will be excluded from the study)
- Pacemaker dysfunction (very rare; subjects with pacemakers will be excluded from the study)

- Skin burns (very rare)
- Tinnitus and hearing loss (very rare)
- Quench (very rare)
- Pain or discomfort associated with administration of contrast
- Allergic reaction to gadolinium (rare)
- Gadolinium-Associated Nephrogenic Systemic Fibrosis (very rare)

Potential AEs associated with moderate sedation during procedure:

- Over sedation (less possible)
- Nausea, vomiting, and/or allergic reaction to medications / anaphylaxis (rare)
- Respiratory failure, myocardial infarction, and death (rare)

Potential risks associated with study enrollment and ancillary study procedures:

- Discomfort due to blood draws required for the study (possible)
- Minor local discomfort due to the pressure of the ultrasound transducer on the skin during arterial access (possible)
- Inconvenience at having to return for follow-up visits (possible)
- Discomfort, Thrombophlebitis, bruising, bleeding, blood clot, presyncope or syncope (i.e. fainting) due to blood draws required for the study (less possible)
- Psychological discomfort from clinical trial enrollment and completing study questionnaires (less possible)
- Infection from blood draw for lab tests (rare)
- Loss of confidentiality of medical records (rare)

Risk minimization:

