6.1 Study Procedures/Evaluations

6.1.1 Study Specific Procedures

- Imaging assessment with knee MRA (visits 2, 6, and 8):
 - Baseline and follow-up (at 6 and 24 months) knee MRA will be performed.
- Biological specimen collection (visits 2, 5, 6, 7, and 8):
 - Baseline and follow-up biomarker analysis from blood, urine, and knee aspirate (synovial fluid) will be obtained from participants.
- Administration of questionnaires or other instruments for patient-reported outcomes (visits 2, 5, 6, 7, and 8):
 - VAS questionnaire
 - KOOS questionnaire
 - Self-reported quality of life EQ-5D-5L questionnaire
 - Anchor pain questionnaire
- GAE procedure (visit 3)
- Medical history (visits 2, 5, 6, 7, and 8):
 - Complete medical history will be obtained from medical records if available and/or by interview during clinic visits.
- History of previous and concomitant treatment (visits 2, 5, 6, 7, and 8):
 - Knee injections and frequency
 - Medication history. Will focus on medications currently taken for the treatment of knee pain; including prescription and over-the-counter medications for pain.
 - Physical therapy and frequency
 - Weight loss / gain
- Focused physical examination (visits 2, 5, 6, 7, and 8):
 - Vital signs (temperature, blood pressure, heart rate, oxygen saturation, height, weight, BMI)
 - Focused knee examination.

Note: A discussion of the results of any study specific procedures (e.g., radiographic or other imaging or laboratory evaluations) will be provided to participant after the completion of the study unless this information represents a significant health-related issue.

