6.3 Study Schedule

6.3.1 Screening (visit 1; Day -30 to -2)

In rheumatology, orthopedic, or vascular and interventional radiology clinic

- Obtain informed consent of potential subject
- Provide a copy of informed consent and key information sheet to subject
- Review subject's eligibility based on eligibility criteria
- Schedule study visits for eligible participants

Note: if subject prefers, visits 1 and 2 can be combined and procedures of these visits may be performed on the same day after completion of screening and obtaining informed consent.

Those candidates who are disqualified from study entry will be logged into the Screening Log with a reason for no study entry. A copy of the consent will be provided to the subject and the original filed in the study files.

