6.3.4.2 Follow up visit at 3-month (Visit 5, Day 90 ± 10 days)

- Obtain medical history
- Record adverse events as reported by participant or observed by investigator (if applicable)
- Targeted physical exam
- Administration of study questionnaires
- Previous / concomitant treatments, including medical history
- Biospecimen collection (including knee aspiration for synovial fluid collection)

6.3.4.3 Follow up visit at 6 months (Visit 6, Day 180 ± 20 days)

- Obtain medical history
- Record adverse events as reported by participant or observed by investigator (if applicable)
- Targeted physical exam
- Administration of study questionnaires
- Previous / concomitant treatments, including medical history
- Biospecimen collection (including knee aspiration for synovial fluid collection)
- Follow-up knee MRA

6.3.4.4 Follow up visit at 12 months (Visit 7, Day 360 ± 30 days)

- Obtain medical history
- Record adverse events as reported by participant or observed by investigator (if applicable)
- Targeted physical exam
- Administration of study questionnaires
- Previous / concomitant treatments, including medical history
- Biospecimen collection (including knee aspiration for synovial fluid collection)

6.3.4.5 Follow up visit at 24 months (Visit 7, Day 720 ± 40 days)

- Obtain medical history
- Record adverse events as reported by participant or observed by investigator (if applicable)
- Targeted physical exam
- Administration of study questionnaires
- Previous / concomitant treatments, including medical history
- Biospecimen collection (including knee aspiration for synovial fluid collection)
- Follow-up knee MRA

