Anchor questionnaire					X	X	X	
Knee MRA	X ¹					X ³	X ³	
Adverse Events	X		X		X	X	X	
Knee radiograph	X ²							
GAE			X					

- 1- If not previously available (i.e., recent knee MRA **within 3 months** of screening); if MRA cannot be obtained on the same day due to subject preference and/or MRI scheduling related reasons, MRA can be performed anytime between the baseline visit and intervention visit.
- 2- If not previously available (i.e., recent knee radiograph **within 3 months** of screening). Can be performed on a separate day based on appointment availability or subject's preference.
- 3- Post-intervention MRAs can be done on a separate day (visit 6 and visit 8) based on appointment and subject's availability as long as it's performed within the timeframe of the visit.

* Visit 1 and 2 can be combined and performed on the same day.

** Visit 4 (7-day safety visit) can be performed over the phone, telemedicine, or in-person clinic visit determined by subject's preference and need for physical examination.

Baseline samples for biomarker analysis (blood, urine, and synovial fluid) can be done on the day of the procedure prior to initiation of procedure (GAE).

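### No visit tests for pregnancy before GAE fluoroscopy, and the renal exclusion prints its creatinine unit inverted and has no scheduled test

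*Combined protocol and SAP*

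**What the plan says.** **Pregnancy.** Section 4.2 item 7 excludes pregnancy for the whole study period, Section 4.3 says pregnant women will not be recruited, and Sections 4.7.1 and 7.4.4 provide for withdrawal if pregnancy is discovered. Section 4.1 admits patients aged 30 to 85 regardless of gender. The closing note to Section 4.2 lets absence of exclusions be confirmed by an orthopedic investigator, by recent orthopedic notes, or by both.

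**Renal function.** Section 4.2 item 8 excludes "Renal dysfunction as defined by serum creatinine >1.6 dl/mg or eGFR <60 on blood tests obtained within 30 days of procedure".

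**Order of events.** Eligibility is reviewed at visit 1 (Section 6.3.1). Visits 1 and 2 may be merged, in which case "procedures of these visits may be performed on the same day after completion of screening and obtaining informed consent". Note 1 to the Schedule of Events (Section 19) adds that, if not obtained the same day, "MRA can be performed anytime between the baseline visit and intervention visit".

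**Imaging.** Section 6.1.1 states: "Baseline and follow-up (at 6 and 24 months) knee MRA will be performed". Section 1.4.1 describes the knee MRA as contrast-enhanced and lists gadolinium-related nephrogenic systemic fibrosis as a very rare risk.

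**Samples.** The blood and urine in Section 6.2 go to a research laboratory for biomarkers. Section 19 allows the baseline set to be taken on the day of GAE.

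**The concern.** An exclusion is only as good as the step that detects it. For pregnancy the protocol gives the rule and the consequence but no means of finding out. A coordinator could complete every scheduled item and send a participant to fluoroscopy with pregnancy status known only from history or records.

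For renal function the rule does call for a blood result, but no visit list or schedule row assigns it to anyone. Its place relative to the baseline contrast MRA is implied rather than stated, and the creatinine threshold is printed in a unit that reverses its meaning. At stake are avoidable radiation exposure in an unrecognized pregnancy and a clean, auditable eligibility check. The efficacy analysis is not at stake.

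**Working it through.** **1. Is either test ordered anywhere?** The places that could order one are:

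- Section 6.1.1, study-specific procedures: MRA, biospecimens, questionnaires, GAE, history, treatments, examination. No renal or pregnancy test.
- Section 6.1.2, standard-of-care procedures: knee radiograph only.
- Section 6.2, laboratory: blood, urine and synovial fluid for biomarkers only.
- Sections 6.3.1 to 6.3.5, visit lists: no renal or pregnancy test.
- Section 19, procedure rows: eligibility, consent, demographics, history, examination, VAS, KOOS, EQ-5D-5L, previous treatments, venous blood, urine, synovial fluid, anchor questionnaire, MRA, adverse events, radiograph, GAE. That is 17 rows: 0 for creatinine/eGFR and 0 for pregnancy.

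The count uses row labels only, so it does not depend on how the table's columns are aligned.

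**2. Which exposure matters for pregnancy?** Section 1.4.1 gives about 0.003 mSv for a knee radiograph and a mean of 3.0 to 12 mSv for lower-extremity angiography. The ratio is 3.0/0.003 = 1,000 to 12/0.003 = 4,000, so GAE is the exposure to protect. Section 6.3.3 puts GAE within 30 days of visit 2, so a test at visit 2 could be up to 30 days old. Day 0 is the natural point.

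**3. What does the printed creatinine unit mean?** A value in dl/mg is the reciprocal of one in mg/dL. Above 1.6 dl/mg is therefore below 1/1.6 = 0.625 mg/dL, which would exclude low creatinine and admit high. Corrected, the criterion excludes creatinine above 1.6 mg/dL. The alternative limb, eGFR below 60, is unaffected by the unit.

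**4. Must the renal result precede the baseline MRA?** Section 6.3.1 points that way, since same-day procedures follow completed screening. But item 13 of Section 4.2 uses the study MRA itself to look for TKA complications, so eligibility cannot be fully settled before that scan. Note 1 to Section 19 ties the scan only to the interval between baseline and intervention. The order is therefore implied, not fixed. A sample at visit 1 (Day -30 to -2) would satisfy the 30-day window in item 8 and could come before the MRA.

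**The case against.** **Renal testing before GAE is already mandatory.** Item 8 names the analytes, cut-offs and window, and visit 1 requires eligibility to be reviewed. Nobody can properly clear item 8 without the result. This stands: what is missing is an assignment to a visit, not the requirement. The infection criteria in Section 4.2 also cite CRP and ESR without a schedule row, so this is partly the protocol's style. Section 13.3 mentions a Manual of Procedures, not among the documents available here, which might cover the logistics.

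**Known problems can be acted on.** Records are filtered against the criteria and the treating physician gives clearance (Section 4.4). Section 4.7.1 allows discontinuation for a newly developed exclusion or a severe laboratory abnormality. The MRA is omitted for gadolinium contraindications, an open list that could take in renal disease. These work for conditions already known; none orders a test.

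**The pregnancy risk is small.** Patients have had TKA for osteoarthritis with at least nine months of refractory pain, and the quoted dose is the participant's effective dose, not a fetal dose. This also stands, and it limits the weight of the point without supplying a means of detection.

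**A stronger reading a reader might infer** is that the 6- and 24-month contrast MRAs breach a renal-testing rule. If the only result is the one item 8 calls for (Day -30 to 0), its age would be 160 to 200 + 30 = 230 days at visit 6 (180 ± 20) and 680 to 760 + 30 = 790 days at visit 8 (720 ± 40). The documents do not support calling this an error. The 30-day window is set for GAE, and no gadolinium threshold or retest interval is given. Nor can contrast-induced renal dysfunction be cited for these scans, since Section 1.4.1 lists it under angiography.

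**Conclusion.** The point holds as a minor safety improvement. Its core is that the pregnancy exclusion has no scheduled means of detection before a procedure averaging 3.0 to 12 mSv. Alongside it, an operative renal threshold is printed with an inverted unit, and the renal test it requires is not placed at any visit.

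The number of participants affected cannot be estimated: the documents give no pregnancy rate or renal-impairment rate for this population. The conclusion assumes that some eligible participants could be pregnant, which the age and gender criteria allow, and that no unseen manual already orders the tests.

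A reader might take the inverted unit to mean that patients with renal impairment would be admitted. That does not follow, because eGFR below 60 excludes them independently and the intended direction is obvious. Renal checks before the follow-up MRAs are a suggestion only. The primary endpoint, sample size and error rates are unaffected.

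**What to change.** 1. Add a pregnancy test for participants of child-bearing potential on Day 0, with the result known before GAE, in Section 6.3.3 and as a row in Section 19.
2. Correct the creatinine unit in Section 4.2 item 8 to mg/dL.
3. List the item 8 creatinine/eGFR test at visit 1 or 2, within 30 days of GAE, and state that its result must precede any baseline contrast MRA. Unlike the biomarker samples, this one should not be left to Day 0 when a baseline MRA is planned.

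Optional: before the 6- and 24-month MRAs, check renal function by history or by a clinical eGFR sample kept separate from the biomarker tubes, against a threshold the team sets. Note 3 to Section 19 lets these scans fall on another day within the visit window, so they could wait for a result.

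Cost: a protocol amendment with IRB review, minor routine laboratory expense and possibly a few screen failures. The optional step could add a trip, for which Section 14.2 offers no reimbursement, and could delay or omit a few MRAs that feed the synovitis endpoint.

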4.3 Vulnerable Subjects

The study does not intend to recruit vulnerable subjects. The study will not recruit any children, pregnant women, or prisoners.

4.4 Strategies for Recruitment and Retention

Participants will be recruited at the study investigator or sub-investigator clinical practices, via brochures / social media, and through an EPIC search.

Study Investigator Or Sub-Investigator Clinical Practices

A study investigator or sub-investigator will assess the medical record of potential subjects for eligibility and provide eligible participants with information regarding the study during the initial study visit and, if patients are interested, obtain informed consent.

IRB-approved study coordinator or co-investigator will guide interested people through written informed consent. Recruitment is expected to occur over four years. To achieve the primary objective, data from 40 patients will be required (i.e. completed GAE and at least 6 month visit) and the study would accrue 50 patients to account for an attrition rate of 20%.

Only NYULH individuals who are listed on the IRB-approved protocol will approach patients for consent.

Brochures / Social Media

A study brochure [attachment 3] will also be available in NYULH rheumatology, orthopedics, family medicine, and interventional radiology clinics and will be also disseminated on social media (e.g. Facebook, Twitter, blogging) to advertise for the study after IRB approval. The study brochure will include contact information for interested subjects to contact the study coordinator and/or PI.

DataCore/Epic Information for Recruitment

Potential study subjects will often be identified by the orthopedic sub-investigator. This study will utilize EPIC to identify subjects. IRB-approved study personnel will submit a request to NYULH DataCore via iLab after obtaining IRB approval to generate a report. The report will be requested to generate a list of potential subjects with a diagnosis of knee pain post TKA and who meet eligibility criteria from the electronic medical system of NYULH.

The research coordinator(s), PI, and co-investigators will have access to EPIC search results / DataCore report throughout the study active enrollment period. The report request will be submitted twice a month during the course of the study. The list will be filtered to identify patients who meet eligibility criteria listed in this protocol.

The PHIs that will be extracted from the EPIC search will be patient's name, MRN, contact information, and name and contact information of the treating physician (TP). The dataset will be deleted after discontinuation, termination, or completion of the study.

Queries regarding eligible subjects will run during the course of the study until discontinuation, termination, or completion of the study.

Once potential subjects have been identified, a study coordinator or investigator will contact the treating physician (orthopedic surgeon who performed the TKA and following the patient) in person. Once clearance is obtained from treating physician, a study team member will inform the potential subjects about the study using the study brochure [attachment 3] and standard language [attachments 4&5].

Patients may be contacted by email, the MyChart portal, MyChart recruitment tools through DataCore, and/or direct phone call using standard language [attachment 4]. When sending recruitment information by email, SendSafe Secure email will be used to contact patients.

Once contact is made, the IRB-approved study brochure or language included in the approved study brochure (if contact made by phone) will be used to communicate the reason they are being contacted and subjects will be asked if they are interested in participating in this specific study. Should the potential subjects agree, the study team will provide the subjects with information regarding the next steps for participation.

If a subject requests information regarding opting out of further recruitment for all research, subjects will be directed to contact the VIR research coordinator or the PI at [contact] or at the office number [contact]. The contact information will also be available on the study brochure. If patient agrees to participate, he will be scheduled for a clinic visit with one of the investigators (visit 1) to further discuss the study, complete the screening elements, and obtain informed consent.

If a subject requests information regarding opting out of further recruitment for all research, subjects will be directed to contact study coordinator or have subjects contact [contact] or [name].

